11 CRITERIA FOR RESPONSE

11.1 Primary objective: safety

The primary objective is to assess the safety of neoantigen DNA vaccines given alone or in combination with durvalumab.

Assessment of the safety of neoantigen DNA vaccines will include both clinical observation and laboratory evaluation. Safety will be closely monitored after injection with eight or more clinical and laboratory assessments in the first 24 weeks of the trial. The following parameters will be assessed following vaccination:

- (1) Local signs and symptoms
- (2) Systemic signs and symptoms
- (3) Laboratory evaluations, including blood counts and serum chemistries
- (4) Adverse, and serious adverse events

Toxicity will be graded according to the National Cancer Institute Common Terminology Criteria for Adverse Events v4.03.

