10 STUDY CALENDAR

	Screening ^j	Eligibility Re-Check ^f	D1 ^h	D29	D57	D85	D113	D141	D169 ⁿ	EOT ^k	52 Weeks after completion of neoantigen DNA vaccine therapy	Long-term F/U ^e	
Randomization		X ^g											
Durvalumab ^{a,b}						X	X	X	X				
Vaccine ^d			X	X	X	X	X	X					
Concurrent meds	X		X	-----							X		
Physical exam, wt, PS	X	X	X	X	X	X	X	X	X	X			
Vital signs	X	X	X	X	X	X	X	X	X				
Medical History	X	X											
CBC w/diff, plts	X	X	X	X	X	X	X	X	X				
CMP ^c	X	X	X	X	X	X	X	X	X				
TSH, fT3, fT4	X	X				X ^{ab}	X ^{ab}	X ^{ab}	X ^{ab}				
Urinalysis	X	X				X ^{ab}	X ^{ab}	X ^{ab}	X ^{ab}				
ECG (in triplicate)	X	X				As clinically indicated ^a							
PT, aPTT, INR	X	X				As clinically indicated ^a							
Troponins I and T	X	X				Every 4 Weeks before treatment ^a							
AE evaluation ^o			X	-----							X		
Tumor measurements	X	As clinically indicated. Documentation (radiologic) must be provided for pts removed from study for PD.											
Radiologic evaluation	X	Radiologic measurements will be performed as clinically indicated.											
Conf. of persistent disease		X											
B-HCG	X	X	X	X	X	X	X	X					
Hepatitis serologies	X												
HIV testing	X												
Tissue collection	Research bx or surgical specimen or both												
Blood for sequencing	X												
Blood for immune monitoring ^p		X ^m	X	X	X	X	X		X		X		
a: Only if randomized to receive durvalumab													
b: To begin on Cycle 4, if neoantigen-specific T cell responses are detectable only if randomized to get Durvalumab													
c: Albumin, alkaline phosphatase, total bilirubin, bicarbonate, BUN, calcium, chloride, creatinine, glucose, potassium, total protein, SGOT [AST], SGPT [ALT], sodium													

d: +/- 7 days with at least 21 days between each injection
e: Annually for 5 years (\pm 2 weeks)
f: After completion of SOC therapy
g: After confirmation of eligibility and manufacture of vaccine
h: After completion of SOC therapy
j: May take place up to 28 days prior to registration.
k: Within 30 days of last day of study treatment
m: After the end of SOC chemotherapy
N: Durvalumab group only
O: In addition to completing an AE assessment at the vaccine dosing visit, an additional follow-up between 24-48 hours after vaccination must be performed (can be performed by phone). AE assessment and SAE reporting continues until 90 days after the last dose of Durvalumab or until time of initiation of other anticancer therapy, whichever occurs first.
p: \pm 28 days

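### Section 11.1 promises eight or more clinical and laboratory assessments, but the calendar schedules 5 or 6 post-injection visits with blood counts and chemistry, and footnote N, read literally, leaves the vaccine-alone arm none after the Day 141 visit

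*Combined protocol and SAP*

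**What the plan says.** Safety is the primary objective, and it is to be assessed by both clinical observation and laboratory evaluation (Sections 1.1 and 15.1.1). Section 11.1 quantifies the effort: "Safety will be closely monitored after injection with eight or more clinical and laboratory assessments in the first 24 weeks of the trial". The parameters it lists for assessment after vaccination include "Laboratory evaluations, including blood counts and serum chemistries".

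The calendar in Section 10 gives the blood-count row as "CBC w/diff, plts X X X X X X X X X": nine marks, at Screening, Eligibility Re-Check and Days 1, 29, 57, 85, 113, 141 and 169. The CMP row has the same nine. The examination row, "Physical exam, wt, PS X X X X X X X X X X", has ten; the extra one is the end-of-treatment visit, timed by "k: Within 30 days of last day of study treatment". The Day 169 column carries "N: Durvalumab group only". After baseline, the thyroid, urinalysis and troponin rows carry "a: Only if randomized to receive durvalumab".

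Footnote O of the calendar requires an adverse-event follow-up 24-48 hours after each vaccination and allows it by phone.

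Day 169 appears elsewhere with no arm restriction: in the blood-collection list of Section 11.3.1, in the between-arm power calculation of Section 15.2.1, and on the Immune Monitoring Form in Section 16. Section 15.3.1 promises boxplots of laboratory values at baseline and during and after protocol therapy.

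**The concern.** The commitment in 11.1 describes how intensively the primary objective will be monitored. If an assessment means a visit with both a clinical and a laboratory part, the calendar does not deliver it in either arm.

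The gap is not spread evenly over the schedule. In the vaccine-alone arm it falls after the sixth and last vaccination. That arm is the one that shows laboratory effects of the vaccine without durvalumab. If it has no scheduled CBC or CMP after the final vaccination visit, the post-therapy laboratory summaries of 15.3.1 have nothing to show for it.

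Site staff following the calendar also cannot tell whether a vaccine-alone patient should attend Day 169 at all, although the immune analysis needs that patient's blood there.

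**Working it through.** **Inputs.** Vaccinations are on Days 1, 29, 57, 85, 113 and 141 (Section 8.1). Examination, CBC and CMP marks, the Day 169 footnote and the end-of-treatment timing come from Section 10. Twenty-four weeks after Day 1 is 1 + 24 × 7 = Day 169. The stated figure to reproduce is eight or more.

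**Count.** Columns after the first injection and up to Day 169 that carry both an examination and CBC/CMP:

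- Vaccine alone: Days 29, 57, 85, 113, 141 = 5.
- Durvalumab: the same five plus Day 169 = 6.

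**Other ways of counting.**

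| Rule | Vaccine alone | Durvalumab |
|---|---|---|
| Post-injection visits with examination and CBC/CMP | 5 | 6 |
| Adding the Day 1 visit | 5 + 1 = 6 | 6 + 1 = 7 |
| Adding Day 1 and the pre-treatment re-check | 5 + 1 + 1 = 7 | 6 + 1 + 1 = 8 |
| First row plus the end-of-treatment examination (no CBC/CMP) | 5 + 1 = 6 | 6 (visit falls after Day 169) |
| First row plus the six 24-48 hour contacts (no laboratory part) | 5 + 6 = 11 | 6 + 6 = 12 |
| First row if both arms have Day 169 CBC/CMP | 5 + 1 = 6 | 6 |

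The end-of-treatment visit is due by Day 141 + 30 = 171 in the vaccine-alone arm and by Day 169 + 30 = 199 in the durvalumab arm. The only laboratory-based count that reaches eight does so in one arm and includes the re-check, which precedes any injection. Day 169 lies exactly at the 24-week limit, so a late visit within its window would fall outside it.

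**After the last vaccination.** CBC/CMP scheduled after the Day 141 visit: none for vaccine alone, one (Day 169) for durvalumab. The end-of-treatment column has an examination but no CBC, CMP or vital signs. The blood drawn 52 weeks after vaccination is research blood for immune monitoring, not a safety panel.

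**Day 169, side by side.** Footnote N limits the column to the durvalumab group. The immune-monitoring row has a mark in that same column. Section 11.3.1 lists Day 169 blood for all patients, 15.2.1 compares the arms on Day 169 measures, and Section 16 puts Day 169 on the Immune Monitoring Form. A between-arm comparison at Day 169 needs blood from both arms, so these passages cannot all hold as written.

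**The case against.** The strongest reply is that 11.1 does not say every assessment must include a laboratory test. As a pooled total of clinical and laboratory contacts, the promise is met with room to spare: 11 and 12. The follow-up contacts are mandatory, and Section 9.2 repeats them. This stands. A reader might infer that the promise fails on every reading, and the documents do not support that. What they support is that eight is not reached by visits with laboratory tests.

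Second, the gap after the last vaccination depends on how footnote N is read. If it marks only durvalumab-specific items, the existing Day 169 CBC/CMP marks cover both arms and the gap disappears. It also depends on Day 141 blood being drawn before the injection. Only the troponin row specifies sampling before treatment; the CBC and CMP rows give no order. Both conditions are real and belong in the statement of the point. They are also a reason to settle the footnote.

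Third, a reader might infer that extra testing with durvalumab biases a between-arm safety comparison. The plan does not make that comparison. Section 15.3.1 calls the safety data descriptive, specifies no between-arm safety test, and plots laboratory values by time point, so an additional visit appears as its own time point. Running thyroid, urinalysis and troponin tests only where durvalumab is given is a design choice. What remains is a labelling matter.

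Finally, the Day 169 immune draw has a window of ±28 days (footnote p), so it is not by itself a fixed safety visit. The fix therefore has to name the visit.

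**Conclusion.** The point holds as an internal inconsistency with a practical consequence. Post-injection visits with CBC/CMP number 5 (vaccine alone) and 6 (durvalumab) against a stated eight or more. The larger number requires contacts that have no laboratory part.

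Followed literally, footnote N leaves the vaccine-alone arm with no scheduled CBC/CMP after the Day 141 visit, and so without the post-therapy laboratory values that 15.3.1 expects. This assumes that the footnote governs the whole column and that Day 141 blood precedes the injection. It does not mean that the sixth dose goes unobserved: the 24-48 hour contact, the end-of-treatment examination and adverse-event evaluation still follow it.

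The conflict over who attends Day 169 depends on neither assumption about the laboratory gap. It arises because footnote N and Sections 11.3.1, 15.2.1 and 16 treat the same visit differently. No planned test or estimate depends on the figure eight, and no distortion of a safety comparison has been shown. The reasons to act are that laboratory safety belongs to the primary objective and that the repair is small.

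**What to change.** - **Section 10:** state that both arms attend Day 169 and limit footnote N to the durvalumab-specific items, so that the CBC and CMP already marked in that column apply to both arms. This brings the calendar into line with 11.3.1, 15.2.1 and the Immune Monitoring Form. State also whether CBC and CMP are drawn before or after the injection.
- **Section 11.1:** replace eight or more with the number of laboratory visits actually scheduled after the first injection, which is 6 in each arm after the change above. If the 24-48 hour contacts are to be cited, count them separately as clinical contacts.
- **Section 15.3.1:** label thyroid, urinalysis and troponin results after baseline as ascertained in the durvalumab arm only.

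The cost is wording, plus one routine blood count and chemistry panel for about 12 patients (24 randomized 1:1, so 24 / 2 = 12) at a draw the plan already lists. The stated assessment count becomes less favourable. Because 6 is still below 8, the 11.1 wording needs correcting however Day 169 is resolved.

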11.2 Secondary objective: neoantigen-specific T cell response

The secondary objective is to measure the neoantigen-specific T cell response to neoantigen DNA vaccines given alone, or neoantigen DNA vaccines plus durvalumab. The immune response will be measured in the peripheral blood by luminex assay, ELISPOT, and multiparametric flow cytometry.

11.3 Neoantigen-specific T cell response

The secondary objective is to assess the neoantigen-specific T cell response to the neoantigen DNA vaccine. To accomplish this goal, peripheral blood will be collected at multiple time points before and after vaccination. After peripheral blood and primary breast cancer tissue processing and storage, various assays will be used to assess the neoantigen-specific T cell response. Unless otherwise noted below, biologic specimens will be analyzed simultaneously upon completion of the vaccination protocol in order to minimize assay-to-assay variation.

11.3.1 Tumor tissue and peripheral blood processing

Processing of tumor: The tumor will be sampled prior to initiation of therapy.

Tumor from the research biopsy will be prioritized for tumor exome and tumor cDNA-capture sequencing in order to identify tumor-specific mutant antigens and produce the neoantigen DNA vaccine. The cores will be placed in complete RPMI or equivalent media solution on ice and transported to [name] laboratory (CSRB, room 6664). Upon receipt by the lab, the tissue will then be prioritized for embedding in optimal cutting temperature (OCT) compound. The remaining cores will be placed into formalin for subsequent paraffin embedding (FFPE).

Cryomold will be filled slowly to the top with OCT compound. Tissue will be gently submerged into the OCT compound in the cryomold. OCT will then be hardened by placement on dry ice or in the vapor phase of liquid nitrogen. After hardening, the mold will be placed in a container and transferred to a -80°C freezer for storage. The frozen tissue will be transferred to the Laboratory of Translation Pathology (LTP, BJC-Institute of Health, Room 5110) or the CHiIPs Immunomonitoring Laboratory for storage.

In addition to tumor from a research biopsy, tumor from surgical specimens may be acquired.

Processing of peripheral blood: Blood samples will be collected at the following time points: baseline, following completion of standard of care therapy, and Days 1, 29, 57, 85, 113, 169 and at 52 weeks after completion of neoantigen DNA vaccine therapy. Seventy mL of peripheral blood will be collected in 7 green top heparinized tubes by venipuncture (BD Vacutainer® sodium heparin, REF 367874, approximately 10 mL each for a total of approximately 70 mL needed total) The research patient coordinator will transport the blood to the laboratory of [name] located in the Clinical Sciences

Research Building, Room 6664. PBMC will be obtained by Ficoll-Hypaque gradient centrifugation and cryopreserved in 10% DMSO in fetal bovine serum according to standard procedures. Plasma will also be collected and stored for the various immunologic testing to be performed.

11.3.2 Neoantigen identification

DNA will be isolated from PBMC by the CHIIPs IML or [name] laboratory personnel for exome sequencing at The Genome Institute. To identify somatic mutations, DNA and RNA will be extracted from OCT-embedded tumor tissue. The OCT block will be sectioned for H&E staining by the CHIIPs IML and tumor-rich areas will be marked by a trained pathologist. Tumor cells will be macrodissected with or without laser capture, and DNA and RNA will be extracted. Tumor DNA and RNA will undergo tumor exome and tumor cDNA-capture sequencing, respectively, at the McDonnell Genome Institute.

The first step in the sequencing pipeline is exome sequencing of breast cancer and normal DNA. Exome fragments are captured using Nimblegen's "VCRome" exome capture reagent. Background DNA is washed away while the bound exome DNA is eluted and sequenced. Separate libraries are made from the breast cancer and normal DNA and processed independently. Exome sequencing is performed using the Illumina platform.

Exome sequences from breast cancer and normal DNA are compared separately to the human reference sequence and then to one another to identify somatic variation. VarScan 2 software is used to detect misaligned sequences and identify structural variants in the breast cancer DNA.

The second step in the sequencing pipeline is cDNA-capture sequencing. To validate the results of the exome sequencing, and confirm expression of the somatic mutations in the breast cancer, cDNA-capture sequencing of the breast cancer RNA will be performed. cDNA-capture sequencing is very similar to RNA sequencing, but cDNA is captured prior to sequencing to enrich for mRNA. cDNA-capture sequencing is a sensitive and accurate methodology to detect expression of somatic mutations at the mRNA level in breast cancer. cDNA-capture sequencing is performed using the Illumina platform.

We have developed and optimized an epitope prediction algorithm for the identification and prioritization of neoantigens. This optimized epitope prediction algorithm is described below and in our previous publications [19, 96]. We have established this algorithm in collaboration with [name], an internationally-known expert in tumor immunology [20, 80-87]. [name] and [name] were one of the first to use next generation sequencing technologies to identify neoantigens, demonstrating that these antigens are important tumor rejection antigens [20]. [name], [name], and [name] have now optimized the epitope prediction algorithm and have demonstrated that cancer vaccines targeting neoantigens are associated with antitumor immunity [19].

The goal of the optimized epitope prediction algorithm is to identify neoantigens and quantify the neoantigen load. The algorithm uses a combination of binding algorithms and processing algorithms.

Mutations that are expressed in the breast cancer will be identified using the sequencing pipeline outlined above. The predicted amino acid sequences corresponding to the expressed mutations will be pipelined through three class I MHC epitope-binding algorithms provided by the Immune Epitope Database and Analysis Resource (<http://www.immuneepitope.org>): (i) Stabilized Matrix Method (SMM) [90], (ii) Artificial Neural Network (ANN) [91], and (iii) NetMHCpan [92].

A prioritized list of binding epitopes (i.e. $IC_{50} < 500$ nM) will be generated after calculating the median binding affinity value for each mutant sequence (affinity value expressed as $1/IC_{50} \times 100$).

11.3.3 Neoantigen-specific T cell analysis

Peripheral blood will be processed and stored as PBMC and plasma. A frozen aliquot will be used for DNA isolation for both exome sequencing and HLA typing (the latter to be performed by ProImmune). The remainder of the samples will be used to analyze the immune response to neoantigen DNA vaccine alone vs. neoantigen DNA vaccine + durvalumab. We hypothesize that these two therapies will generate durable, neoantigen-specific CD4 and CD8 T cell responses, and affect the levels of immunomodulatory elements within the peripheral blood. We propose the following assays.

Multi-parametric flow cytometry will be used to measure an increase in polyclonal, activated T cells (CD3, CD4, CD8, HLA-DR, Ki67, PD-1, perforin, granzyme A/B), neoantigen-specific T cells (CD3, CD4, CD8,

MHC class I tetramers, MHC class II tetramers as described above) that persist over time (CD45RA, CD45RO, CCR7, CD27, CD28, CD95, CD58), and immunomodulatory elements (regulatory T cells: CD3, CD4, Foxp3, CD25; inflammatory monocytes, granulocytes: CD45, CD11b, CD115, CCR2, CD14, CD15) over various time points.

For functional analysis, Luminex and ELISPOT assays will be performed on PBMC using short peptides that mimic the minimal neoantigen epitope incorporated by the DNA vaccine with which the respective patient was vaccinated. The Luminex assay will be performed in conjunction with the Immune Monitoring Laboratory. ELISPOT assay will be performed as previously described [97-101] on PBMC from the subjects at all time points for IFN- γ . PBMC will be plated at various concentrations started at 300,000 cells per well, in triplicate, following the protocol previously described by [name] and colleagues for detection of breast cancer-specific T cells. PBMC will be co-cultured with the short peptides. As negative controls, PBMC will be incubated in medium alone or stimulated with matching wild-type peptides. As a positive control, we will include a mix of viral peptides (CEF) which contains immunodominant epitopes for multiple common MHC class I alleles from influenza virus, cytomegalovirus, and Epstein-Barr virus. After 24-48 hours, the plates will be developed and the spots counted in an ImmunoSpot Series I analyzer (Cellular Technology).

12 REMOVAL OF SUBJECTS FROM PROTOCOL THERAPY

12.1 Removal of subjects from protocol therapy

Subjects may be removed from protocol therapy if any one or more of the following events occur:

- (1) Development of progressive or recurrent disease requiring systemic treatment or radiation therapy;
- (2) Intercurrent illness that prevents further administration of protocol therapy;
- (3) Pregnancy;
- (4) Type 1 hypersensitivity reaction associated with protocol therapy;
- (5) Grade 2 systemic or injection site adverse event classified as possibly, probably, or definitely associated with protocol therapy that does not resolve to at least grade 1 prior to the next scheduled treatment;
- (6) Grade 3 or 4 systemic or injection site adverse event classified as possibly, probably, or definitely associated with protocol therapy;
- (7) Grade ≥ 3 infusion reaction;
- (8) Any significant autoimmune disease or phenomena presumed to be related to protocol therapy;
- (9) Subject refusal to continue protocol therapy and/or observations;
- (10) Significant protocol violation or noncompliance, either on the part of the subject or investigator(s);
- (11) The principal investigator or study sponsor believes it is in the subject's best interest to discontinue participation in the study;
- (12) Administrative reasons, e.g., study termination by the principal investigator, Siteman Cancer Center, HRPO, FDA, or other group.

Please note that even if a subject is removed from protocol therapy, they will continue to be followed for adverse events.

12.2 Voluntary subject withdrawal

The subject has the right to voluntarily withdraw from the study at any time for any reason without prejudice to her future medical care by the physician or at the institution.

For any subject who withdraws consent, the date and reason for consent withdrawal should be documented. Subject data will be included in the analysis up to the date of the consent withdrawal.

12.3 Procedure for discontinuation

The procedure to be followed at the time a subject either discontinues participation or is removed from the study is:

- (1) Check for the development of adverse events.
- (2) Complete the End-of-Study form and include an explanation of why the subject is withdrawing or withdrawn.
- (3) Attempt to perform follow-up evaluations as outlined above.

13 REGULATORY AND REPORTING REQUIREMENTS

The entities providing oversight of safety and compliance with the protocol require reporting as outlined below. Please refer to 20.4 for definitions and 20.5 for a grid of reporting timelines.

Adverse events will be tracked from start of treatment through 90 days after the last dose of Durvalumab or until initiation of new anticancer therapy, whichever comes first. All adverse events must be recorded on the toxicity tracking case report form (CRF) with the exception of:

- Baseline adverse events, which shall be recorded on the medical history CRF

Refer to the data submission schedule in Section 16 for instructions on the collections of AEs in the EDC.

Reporting requirements for Washington University study team are found in section 13.1.

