4.6 Randomization

Twenty-four patients will be enrolled. Patients will be randomized for participation in a 1:1 ratio to receive either neoantigen DNA vaccine alone or neoantigen DNA vaccine plus durvalumab. The randomization table will be generated using the SAS program PROC PLAN. Randomization will take place after the manufacture of the vaccine and after eligibility has been reconfirmed.

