8.2 Durvalumab administration

For patients who are randomized to the neoantigen DNA vaccine plus durvalumab arm, the neoantigen-specific T cell response will be assessed prior to Day 85. If a neoantigen-specific T cell response is present, durvalumab will be started on Day 85, and will be administered Q4W (\pm 7 days) at a dose of 1500 mg over the course of 60 minutes. If a neoantigen-specific T cell response is not present, these patients will be replaced but may continue to receive the neoantigen DNA vaccine on study. They will not be transferred to the vaccine-only arm.

On days when subjects receive both vaccine injections and durvalumab infusions, they will receive the vaccine first, followed by observation for 30 minutes, followed by administration of durvalumab. Subjects will be monitored before, during and after the infusion with assessment of vital signs at the times specified in the Schedule of Assessment. Subjects are monitored (pulse rate, blood pressure) every 30 minutes during the infusion period (including times where infusion rate is slowed or temporarily stopped). Every effort should be made to give durvalumab and vaccine on the same day.

If weight falls to 30 kg or less, durvalumab will no longer be administered.

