8.3 Replacement of patients

Patients who initially meet eligibility criteria and have a vaccine manufactured but either fail eligibility re-check based on durvalumab-specific criteria (but are still able to receive neoantigen vaccine safely) or are randomized to receive durvalumab but do not experience a neoantigen-specific T cell response (and thus

cannot receive durvalumab) may receive the neoantigen DNA vaccine but will be considered inevaluable and will be replaced. Safety and response data will be collected and analyzed separately.

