13.1.4 Reporting to AstraZeneca

All SAEs will be reported, whether or not considered causally related to the investigational product, or to the study procedure(s). The reporting period for SAEs is the period immediately following the time that written informed consent is obtained through 90 days after the last dose of durvalumab or until the initiation of alternative anticancer therapy. The investigator and/or Sponsor are responsible for informing the Ethics Committee and/or the Regulatory Authority of the SAE as per local requirements.

The investigator and/or sponsor must inform the FDA, via a MedWatch form, of any serious or unexpected adverse events that occur in accordance with the reporting obligations of 21 CFR 312.32, and will concurrently forward all such reports to AstraZeneca. A copy of the MedWatch report must be emailed to AstraZeneca at the time the event is reported to the FDA. It is the responsibility of the sponsor to compile all necessary information and ensure that the FDA receives a report [according to the FDA reporting requirement timelines](#) and to ensure that these reports are also submitted to AstraZeneca at the same time.

* A **cover page** should accompany the **MedWatch** form indicating the following:

- “Notification from an Investigator Sponsored Study”
- The investigator IND number assigned by the FDA
- The investigator’s name and address
- The trial name/title and AstraZeneca ISS reference number (ESR-16-12613)

* Sponsor must also indicate, either in the SAE report or the cover page, the **causality** of events **in relation to all study medications** and if the SAE is **related to disease progression**, as determined by the principal investigator.

* **Send SAE report and accompanying cover page by way of email to AstraZeneca's designated mailbox: [contact]**

If a non-serious AE becomes serious, this and other relevant follow-up information must also be provided to AstraZeneca and the FDA.

Serious adverse events that do not require expedited reporting to the FDA still need to be reported to AstraZeneca preferably using the MedDRA coding language for serious adverse events. This information should be reported on a monthly basis and under no circumstance less frequently than quarterly.

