13.1.4.1 Reporting of deaths to AstraZeneca

All deaths that occur during the study or within the protocol-defined 90-day post-last dose of durvalumab safety follow-up period must be reported to AstraZeneca as follows:

- Death that is clearly the result of disease progression should be documented but not reported as an SAE
- Where death is not due (or not clearly due) to progression of the disease under study, the AE causing the death must be reported to AstraZeneca as an SAE within **24 hours**. The report should contain a comment regarding the co-involvement of progression of disease, if appropriate, and should assign main and contributory causes of death.
- Deaths with an unknown cause should always be reported as an SAE.

Deaths that occur following the protocol-defined 90-day post-last dose of durvalumab safety follow-up period will be documented but will not be reported as an SAE.

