16.1 Adverse Event Collection in the Case Report Forms

All adverse events that occur beginning with start of treatment (minus exceptions defined in Section 13) must be captured in the Toxicity Form. Baseline AEs should be captured on the Medical History Form.

Participant death due to disease progression should be reported on the Toxicity Form as grade 5 disease progression. If death is due to an AE (e.g. cardiac disorders: cardiac arrest), report as a grade 5 event under that AE. Participant death must also be recorded on the Death Form.

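### The written AE/SAE collection rules end on a durvalumab clock, never refer to the last vaccine dose, and appear to conflict with the calendar's AE row, so the window behind the primary safety percentages is unsettled

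*Combined protocol and SAP*

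**What the plan says.** Three passages state when collection ends.

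- Section 13: adverse events are "tracked from start of treatment through 90 days after the last dose of Durvalumab or until initiation of new anticancer therapy, whichever comes first".
- Section 10, footnote O, attached to the AE evaluation row: assessment of AEs and "SAE reporting continues until 90 days after the last dose of Durvalumab or until time of initiation of other anticancer therapy, whichever occurs first".
- Section 13.1.4, on SAE reports to the durvalumab supplier: the period starts once consent "is obtained through 90 days after the last dose of durvalumab or until the initiation of alternative anticancer therapy".

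Section 13.1.4.1 then covers "All deaths that occur during the study or within the protocol-defined 90-day post-last dose of durvalumab safety follow-up period", treating the durvalumab-based period as the protocol's safety follow-up. Section 16.1 gives a start but no end: "All adverse events that occur beginning with start of treatment (minus exceptions defined in Section 13) must be captured in the Toxicity Form".

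On allocation, Section 4.6 says: "Patients will be randomized for participation in a 1:1 ratio to receive either neoantigen DNA vaccine alone or neoantigen DNA vaccine plus durvalumab". Section 8.3 adds two groups who may be vaccinated without durvalumab: those who fail the durvalumab-specific eligibility re-check, and durvalumab-arm patients without a T cell response. Both are replaced, and for them "Safety and response data will be collected and analyzed separately".

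The AE evaluation row in Section 10 carries no arm restriction. In the extracted text it starts at Day 1 and appears to end under the column for 52 weeks after vaccination is complete.

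Section 15.3.1 defines the primary result: the number and percentage of subjects with each type of event, by severity and relationship. It states no observation window.

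**The concern.** A crude percentage of patients with an event depends on how long they were watched. A clock that starts from the last durvalumab dose means nothing for a patient who never had one, and by design that is half of the randomised patients. If one arm is closed at a durvalumab-based date and the other stays open, or is closed at a date the site chooses, the two sets of percentages describe different lengths of follow-up. Reactions soon after injection are not at risk, because footnote O requires a contact 24 to 48 hours after each vaccination. The question concerns later events.

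**Working it through.** **Inputs.** Vaccine is given on Days 1, 29, 57, 85, 113 and 141 (Section 8.1). Durvalumab is given on Days 85, 113, 141 and 169, up to four doses (Sections 8.7 and 10). Twenty-four patients are allocated 1:1 (Section 4.6). All days below are nominal.

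**Step 1. Written rule, four durvalumab doses.** End = last durvalumab day + 90 = 169 + 90 = Day 259. That is 259 − 141 = 118 days after the last vaccination.

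**Step 2. Written rule, no durvalumab.** There is no last durvalumab dose, so the first limb cannot be computed. The other limb is new anticancer therapy, which may never start. By design this applies to 24 × 1/2 = 12 patients, plus any in the Section 8.3 groups, whose number is unknown.

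**Step 3. Calendar row.** Counting columns from the header, the AE row's marks fall at Day 1, a dashed line from Day 29, and the 52-week column. As a check on the alignment, the immune-monitoring row read the same way gives Days 1, 29, 57, 85, 113, 169 and 52 weeks, which matches the blood-sampling list in Section 11.3.1. If the reading is right, the row ends at 141 + 364 = Day 505.

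**Step 4. Row against footnote.** For a four-dose patient, 505 − 259 = 246 days. The footnote is attached to that row, so both cannot govern.

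| Patient | Section 13 and footnote O | AE row, if read correctly |
|---|---|---|
| Vaccine + 4 durvalumab doses | Day 259 | about Day 505 |
| Vaccine alone | no computable end | about Day 505 |

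**Step 5. Could other text supply the missing end?** The synopsis gives at least 12 months of follow-up after last treatment, and Section 8.8 gives 52 weeks or death. Sections 8.7 and 12.1 keep patients in follow-up after treatment stops. Section 8.8 also follows patients removed for unacceptable events to resolution or stabilisation. None of these sets a cut-off for AE collection, and no section gives a vaccine-based end for SAE reporting.

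**Step 6. Edge case within the durvalumab arm.** Section 8.2 says: "If weight falls to 30 kg or less, durvalumab will no longer be administered". It does not say that vaccination stops. After a single dose the written rule would end at 85 + 90 = Day 175, which is 175 − 141 = 34 days after a Day 141 vaccination. This needs durvalumab to stop while vaccination goes on, and is unlikely to be common.

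**Step 7. Grading version, a separate matter.** Section 20.4 prescribes CTCAE v5.0 for all toxicity reporting. Sections 9.3, 15.1.1, 15.3.1, 20.3 and others name v4.03.

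**The case against.** The strongest reply is the calendar. Its AE row applies to both arms and, on the column count, gives an end that is both fixed and vaccine-based. If it governs, everyone is observed to the same point. This stands to a large extent. A reader might infer that the protocol contains no end at all for vaccine-alone patients, and the row tells against that. It does not settle the matter, because the footnote on that row and Section 13 both say something else, and the row does not set an SAE reporting period.

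A reader might also infer that late events in the vaccine-alone arm go uncollected, or that the comparison favours one arm. The documents do not support either. Read literally, the 90-day limb never triggers without durvalumab, so tracking stays open. That is an undefined end and not an early one.

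Three smaller replies also have force. Section 13.1.4 and its subsections concern the durvalumab supplier, where a durvalumab clock is natural, and the death rule there also covers deaths during the study. The protocol does use vaccine anchors elsewhere: death within 30 days of vaccination is a halt criterion (Section 14.1), and contraception runs to one year after the last vaccine dose (Section 8.5). These show that such an anchor is feasible, but they do not define AE collection. Finally, Section 15.3.1 is descriptive and plans no between-arm safety test, so a common-window table by arm goes somewhat beyond correcting an error.

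**Conclusion.** The point holds as an inconsistency in the definition of the primary safety result and should be corrected. The written rules omit the vaccine and give no computable end for about 12 of 24 patients. They also appear to conflict with the calendar row, by 246 days for a four-dose patient. Whether the AE percentages end up covering unequal windows depends on which text the site follows. The size and direction cannot be derived, and there is no imbalance if the calendar row is applied to all. The Section 8.3 patients share the gap but are analysed separately.

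This rests on nominal visit days and on a column count in extracted text. If the final mark in the AE row is misplaced, the calendar no longer supplies an end and the gap in the written rules stands unrelieved.

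The CTCAE conflict is real but minor. A reader might take it as a source of bias between arms. It is not, since it affects both alike and Section 15.3.1 itself names v4.03 for the tables. It matters because the halt criteria (Section 14.1) and removal criteria (Section 12.1) turn on grade.

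**What to change.** Confirm the AE row on the original calendar page. Then reconcile that row, footnote O, Section 13, Section 13.1.4 and Section 16.1, and align Section 13.1.4.1, so that one AE/SAE collection end applies to every treated patient. Tie it to the last dose of any study agent or to a fixed day, as the sponsor chooses, without shortening any collection already specified.

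In Section 15.3.1, tabulate events by arm over a common, pre-stated window and list later events separately. A cut-off before Day 259 would leave part of the 90-day post-durvalumab period outside the main table for a four-dose patient, so the separate listing must cover it. The planned listing already records onset and duration, so no new data items are needed.

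As a separate correction, reconcile Section 20.4 with the other sections to one CTCAE version.

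The cost is protocol wording, a little more analysis and, by assumption, perhaps one or two telephone contacts per patient to reach the common cut-off. No new patients or clinic visits are needed.
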